 - a. An objective improvement in patient physical function from baseline to the time of procedure and 30 days post-procedure.
 - b. Decreased length of stay and improved clinical outcomes and quality of life.

Study design

This is a pilot study involving a cohort of seventy subjects randomized to either participate (treatment group) or not participate (control) in a prehabilitation program prior to undergoing a TAVR. After providing informed consent, subjects will be randomized via REDCap™ to a treatment or control group. Thirty five subjects will be randomized to each group. Subject number and randomization will be assigned by REDCap™. All subjects in this pilot study will be followed from the intake assessment through one year post-procedure.

Study population and recruitment methods

The research coordinator will identify potential TAVR patients using clinic schedules and then conduct a chart review to verify that they meet inclusion/exclusion criteria. Patients will be approached by the research coordinator regarding the study. The research coordinator will verbally explain the study and provide time for questions and discussion. The patient will be provided with a written copy of the consent document to read and review. The research coordinator will set up an additional appointment to assess understanding and verify willingness to participate. The patient will then sign the consent if interested in participation.

Inclusion and exclusion criteria:

Inclusion Criteria

- Subject must be ambulatory (with or without an assist device)
- Subject has severe aortic stenosis and is felt an appropriate candidate for TAVR by the Heart Team.

- Subject requires 6.0 seconds or longer to complete a 15ft walk test
- Subject must be able to move between sitting and standing without assistance from another person.
- Subject has adequate iliac and femoral arterial anatomy to allow for TAVR via transfemoral access
- Subject is 18 years of age or greater
- Subject is willing to give consent and participate in the study

Exclusion Criteria

- Subject is incapable of following instructions
- Subject is unable to meet the minimum required physical therapy visits
- Subject has other medical conditions rendering it unsafe, in the opinion of the Principal Investigator and physical therapy staff, to perform a 6 Minute Walk Test or physical therapy conditioning prior to TAVR
- Subject has significant severe un-revascularized epicardial coronary disease.

Role of subjects

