Comorbidities (all diagnoses codes)	X					X	X
Study comorbidities 
 • Current medications • Pre-existing conditions related to reduced exercise capacity, mobility, and/or balance; including physical disabilities unrelated to aortic stenosis 	X					X	X

6MWT	X		X			X	X
TUG Test	X		X			X	X
FSST	X		X			X	X
Kansas City Cardiomyopathy Questionnaire	X		X			X	X
Date and time of visit		X	X			X	X
Adverse events		X	X*			X	X
• MACE							
• Syncope							
• Falls and musculoskeletal adverse events							
• Adverse events from other complications							
• Serious adverse events, including those that require hospitalization							
Type and size of valve used for TAVR				X			
Adverse events during surgery				X			
Discharge disposition					X		
Length of stay					X		
• In ICU (hours)							
• Total hospital (days)							
Cost of stay (assessed by total charges accrued during hospitalization)					X		
Inpatient readmission information						X	X

*This should be assessed in both groups prior to TAVR to see if the control arm experienced similar adverse events independent of prehab therapy.

Data analysis and Data Monitoring

Evaluate primary, secondary and the safety outcomes (as listed in the protocol) by conducting a data integrity check to assure reliability of the data. Once all data inconsistencies are corrected data analysis should occur. The analysis would compare 2 groups: the study group and the control. Based on the objectives, the data will be analyzed using the required statistical tests; categorical variables would be compared using the Fishers Exact test or Chi-square tests and measurement data would be compared using the independent sample t-test or Mann Whitney U test. All analysis will be evaluated using parametric tests unless the data is not normal in which case non-parametric tests will be used.

As needed interim analysis of primary, secondary and safety outcomes by study group (treatment vs. no treatment) will be conducted. If a decision is made to stop the study early, this limitation should be expressed in any project write-up. If at the conclusion of the assessment of the primary outcome (6 minute walk test) there is a significant difference between the study groups ($p < .05$) a Power analysis will be conducted, and if the Power is greater than 80%, a recommendation to conclude the study could be made – if this is done there is risk of making a type II error and should be shared in any project write up.

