A Data Safety Monitoring Board (DSMB) will monitor all AEs and SAEs to provide safety oversight. DSMB members will not be involved in the study and have no conflict of interest.

Redcap will be the database that will provide data management through a secure, password protected Electronic Data Capture (EDC) system accessible via the Internet. A unique Patient ID will be assigned for each patient enrolled in the study. All pertinent data will be entered by the study site personnel into the electronic Case Report Forms (eCRFs).

Every reasonable effort should be made to complete data entry within 5 business days of data collection. Data review by Quality will occur remotely as well as during on site monitoring. Data discrepancies will be queried and resolved through the EDC system.

The site Principal Investigator or designee must ensure the accuracy and completeness of the recorded data and then provide his/her electronic signature on the appropriate eCRFs. Changes to data previously submitted to the Sponsor will require a new electronic signature to acknowledge/approve the changes.

Risks and risk management

The primary potential physical risks to patients enrolled in this study appear to be adverse cardiac events including dizziness, syncope, angina pectoris, ventricular tachycardia, or sudden cardiac death. Observation studies report exertional dizziness or syncope in patients with severe aortic stenosis suggesting this is a potential risk for patients in this study. Also, ventricular tachycardia has been reported in early studies of patients with severe aortic stenosis undergoing exercise stress tests however this has not been reported in contemporary studies. Other potential physical risks include falling or pain due to exercise.

To mitigate these risks, all potential participants will undergo a complete history and physical examination by a cardiologist prior to enrollment. Any patient determined to be at high risk for adverse clinical event by the cardiologist will be excluded. Also, all participants will undergo standard TAVR non-invasive and invasive testing; this includes: transthoracic echocardiography, transesophageal echocardiography, right and left heart catheterization, and Computer-Assisted Tomography (CAT scan) of the chest, abdomen, and pelvis. Patients with un-revascularized coronary artery disease will not be enrolled in the study.

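### The early-stopping paragraph allows unlimited unadjusted looks at the 6MWT, relies on a post-hoc power check that adds no evidence, and tells authors to disclose the wrong error

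*Combined protocol and SAP*

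**What the plan says.** All of the relevant wording on stopping is in Data analysis and Data Monitoring.

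- Interim looks: "As needed interim analysis of primary, secondary and safety outcomes by study group (treatment vs. no treatment) will be conducted". No number, timing, adjusted threshold or final alpha appears here or elsewhere.
- Trigger: "If at the conclusion of the assessment of the primary outcome (6 minute walk test) there is a significant difference between the study groups" at p<.05, a power analysis follows, and "if the Power is greater than 80%, a recommendation to conclude the study could be made". The effect size and SD for that power analysis are not stated.
- Disclosure: "if this is done there is risk of making a type II error and should be shared in any project write up". A separate sentence asks that early stopping be reported as a limitation, without saying of what kind.
- Oversight: "A Data Safety Monitoring Board (DSMB) will monitor all AEs and SAEs to provide safety oversight". No efficacy role is described for the board or for anyone else.

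Study design sets 35 subjects per arm without a sample-size justification and says "All subjects in this pilot study will be followed from the intake assessment through one year post-procedure". Primary Efficacy Outcomes defines two 6MWT changes: intake to pre-procedure, and intake to one month after. The stopping text does not say which one triggers it.

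**The concern.** There are three statistical faults and two gaps.

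1. **Wrong error.** The recommendation to conclude arises only after the 6MWT null hypothesis has been rejected. A type II error is a failure to reject, so it cannot apply to that comparison.
2. **Open-ended looks.** With the number of looks at the primary outcome left free, the overall type I error has no defined value.
3. **A power check that adds nothing.** Power computed after seeing significance is either a function of the p-value and sample size (observed effect) or of sample size alone (fixed effect). Neither is independent support for stopping.
4. **Gaps.** The text does not name who runs the efficacy look, or say whether concluding the study would end the one-year follow-up.

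A report that follows the paragraph would carry a caveat pointing readers to the wrong error. The study is described as a precursor to a definitive trial, and an inflated effect carried forward could leave that trial too small. Safety is a stated objective and the first hypothesis, and stopping on 6MWT would cut the safety information.

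**Working it through.** **Inputs.** From the protocol: 35 per arm; independent-sample t-test (Mann-Whitney if not normal); trigger p<.05; power above 80%. Assumed, because the protocol is silent: two-sided test, normal data with SD 1, one 6MWT contrast, and the look schedules named below. The protocol gives no power or type I figure to reproduce.

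**Step 1. Power at the observed effect.** In the normal approximation, observed power is Φ(z_obs − 1.960). It exceeds 80% when z_obs > 1.960 + 0.842 = 2.802, that is p < .0051. At exactly p = .05, observed power is Φ(0) = 50%. With the noncentral t (df = 2n − 2, noncentrality d√(n/2)):

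| n per arm | observed d giving 80% power | equivalent p |
|---|---|---|
| 10 | 1.325 | .0083 |
| 18 | 0.961 | .0068 |
| 24 | 0.826 | .0063 |
| 35 | 0.679 | .0059 |

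The power condition is therefore a second, lower p cutoff.

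**Step 2. Power at a fixed effect.** The 80% condition is first met at 17 per arm for 1.0 SD, 21 for 0.9, 26 for 0.8 and 34 for 0.7. For 0.6 SD it is never met by 35 per arm (power 69.7%). Once met, it leaves the cutoff at p<.05.

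**Step 3. Overall type I error** (simulation under the null, 200,000 trials or more per scenario; final test at .05; repeat runs agree within about 0.3 percentage point):

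| Reading of the rule | Looks (n per arm) | Type I error |
|---|---|---|
| Observed-effect power | 18, 35 | about 5.3% |
| Observed-effect power | 12, 24, 35 | about 5.6% |
| Observed-effect power | 10, 15, 20, 25, 30, 35 | about 6.1% |
| Fixed effect 0.8 SD | 26, 35 | about 7.5% |
| Fixed effect 1.0 SD | 20, 25, 30, 35 | about 10% |
| Power condition ignored | two to six looks as above | about 8% to 14% |

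The last row is not the rule as written. It shows what would happen if only the power condition were deleted.

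**Step 4. Size of the reported effect under the observed-effect rule** (mean difference in units of the true SD; ranges span the three look schedules in Step 3):

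| True effect | Trials stopped early | Mean estimate if stopped early | Significant results at 35 per arm, no interim | Mean over all trials |
|---|---|---|---|---|
| 0.3 SD | 3.2–9.1% | 0.96–1.00 | 0.61 | 0.31–0.33 |
| 0.5 SD | 9.8–25.7% | 1.00–1.06 | 0.67 | 0.53–0.56 |

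The average over all trials is nearly right. The exaggeration is in the trials that stop.

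**Step 5. Information lost by stopping at 18 instead of 35 per arm.** Power for a secondary outcome at a true 0.5 SD falls from 54% to 31%. With no events of a given type in the treated arm, the one-sided 95% upper bound is 1 − 0.05^(1/n). This is 1 − 0.05^(1/35) = 8.2% at full size and 1 − 0.05^(1/18) = 15.3% at 18.

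**The case against.** The strongest reply has four parts.

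- **The inflation is modest.** On the most natural reading (power at the observed effect) the type I error is about 5.3% to 6.1%, and the top of that range needs five interim looks that the protocol does not schedule. For a pilot, that is tolerable. This stands: the case does not rest on large inflation.
- **There may be only one look.** The trigger wording can mean a single check once all 6MWT data, which end at one month, are complete. That would remove repeated-look inflation and the early-stopping exaggeration from that sentence. It would not touch the preceding sentence, which permits primary-outcome looks whenever wanted, and it would not make type II the right error.
- **Type II is not baseless.** Ending the whole study early does lower power for the secondary and safety outcomes, as Step 5 shows. This also stands, but the sentence ties its warning to a significant 6MWT result and does not mention the other outcomes.
- **Some disclosure is already required, and the stop is optional.** The limitation sentence is generic and does not name type I error or over-estimation, so it does not correct the specific and wrong statement that follows.

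The unnamed decision-maker and the unclear follow-up are missing detail rather than errors. Study design already commits to one-year follow-up, and the stopping text does not expressly withdraw it.

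**Conclusion.** The concern holds. The error named for disclosure is wrong for 6MWT on every reading of the timing and of the power check. A nominal p<.05 trigger exists, but there is no multiplicity-adjusted boundary and no look schedule, so the overall type I error is undefined. The power condition is either a hidden cutoff near p = .006 to .008 or a sample-size condition; on neither reading is it further evidence.

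The type I inflation is modest if power is taken at the observed effect and larger (about 7.5% to 10%) if a fixed effect of 0.8 to 1.0 SD is used. The heavier costs are an estimate near 1 SD in trials that stop early when the truth is 0.3 to 0.5 SD, and a near-doubling of the zero-event safety bound if the study stops at 18 per arm. These sizes depend on the assumed schedules, normal data and a single 6MWT contrast. The paragraph should be corrected, though it does not undermine the trial if no efficacy stop is made.

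**What to change.** Replace the paragraph as a whole.

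1. Limit unscheduled interim reviews to safety data reviewed by the DSMB.
2. Remove the post-hoc power condition and the p<.05 stopping trigger together. Removing only the power condition would raise the type I error to the 8% to 14% range.
3. Either state that there is no efficacy stopping, or pre-specify one look: sample size, which 6MWT contrast, who reviews it, and an alpha-preserving boundary. One option is Haybittle-Peto, p<0.001 at the interim and .05 at the end.
4. State whether the trigger wording means one analysis on complete 6MWT data, and that follow-up to one year continues regardless.
5. Correct the disclosure: stopping on a significant 6MWT result carries a risk of type I error and an over-estimated treatment effect, and reduces information on secondary and safety outcomes.

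The cost is a one-paragraph amendment and the loss of discretion to stop at p<.05. One Haybittle-Peto look at 18 per arm adds under 0.1 percentage point to the type I error per contrast (4.89% against 4.87% with no interim in the same simulated trials).

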The subject will also perform the following:

- x. 6MWT
- y. TUG Test
- z. FSST
- aa. Kansas City Cardiomyopathy Questionnaire

1-year Follow-up Assessment

All subjects' electronic health records (EHR) will be monitored for one year from the discharge date for the following:

- a. Inpatient re-admission information
- b. Cost of stay (assessed by total charges accrued during hospitalization)
- c. Date and time of visit
- d. Syncope
- e. MACE
- f. Falls and musculoskeletal adverse events

- g. Adverse events from other complications
 - h. Serious adverse events, including those that require a readmission hospitalization
 - i. Mortality
- The subject will also perform the following:
- j. 6MWT
 - k. TUG Test
 - l. FSST
 - m. Kansas City Cardiomyopathy Questionnaire

Research procedures

Patients who qualify for TAVR will be screened by the research coordinator. The research coordinator will also review provider office visit schedules and maintain close contact with the TAVR program coordinator for potential study subjects. The patient will be screened thoroughly ensuring he/she meets all inclusion and exclusion criteria. Once the possible study patient has been identified then the research coordinator will approach the patient and verbally explain the study to them. Adequate time will be provided for questions and answers. The patient will be provided a written copy of the informed consent and time to read it. Once the patient signs the informed consent, the study procedures may commence. The first visit will be the Intake Assessment where the patient will meet with the physical therapist and research coordinator. This assessment will include the 6MWT, TUG test, FSST, KCCQ, patient demographics, subject contact information, and comorbidities. At the completion of this assessment, the patient can be randomized.

The patients randomized to the treatment arm will then be scheduled to begin the prehabilitation part of the study. Subjects will receive a maximum of 12 therapy visits over the next 3 to 5 weeks prior to the surgery date.

Below is a chart that describes what will occur at each required study visit.

	Intake Assessment	Prehabilitation (Treatment only)	Pre-operative Assessment	TAVR	Discharge Assessment	30-day Follow-up Assessment	1-year Post-operative monitoring
Demographics (MRN, name, date of birth, gender, payor, surgery date, surgery type, etc.)	X						
Subject contact information (preferred method, address, phone/text, e-mail, etc.)	X						

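### The coronary exclusion is narrower in the exclusion list than in the risk section, so screening on the list can admit patients whom the stated safeguard bars

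*Combined protocol and SAP*

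**What the plan says.** Two sections of the combined protocol and SAP set a coronary rule for enrolment.

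- **Inclusion and exclusion criteria, exclusion list:** "Subject has significant severe un-revascularized epicardial coronary disease".
- **Risks and risk management**, in the paragraph on how the exercise risks are to be reduced: "Patients with un-revascularized coronary artery disease will not be enrolled in the study".

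Two other sections say how eligibility is checked. Under Study population and recruitment methods, the research coordinator is to "conduct a chart review to verify that they meet inclusion/exclusion criteria". Under Research procedures: "The patient will be screened thoroughly ensuring he/she meets all inclusion and exclusion criteria".

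The risk section adds two related safeguards. A cardiologist examines each potential participant before enrolment, and "Any patient determined to be at high risk for adverse clinical event by the cardiologist will be excluded". The standard work-up for all participants includes "transthoracic echocardiography, transesophageal echocardiography, right and left heart catheterization" and CT imaging.

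**The concern.** The risk section names angina, ventricular tachycardia and sudden cardiac death among the hazards of exercising patients with severe aortic stenosis. Its coronary sentence is one of the measures offered against those hazards, and it is worded as an enrolment rule, not as background. If staff screen on a narrower criterion, an ethics board or a patient reading the risk section is told of a protection that the screening step does not deliver.

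The mismatch also touches an objective. Hypothesis 1 is that monitored physical therapy before the procedure is safe in frail TAVR patients. Whether patients with lesser un-revascularized coronary disease were among those exercised determines whom a favourable safety finding covers. The Objectives section says that the pilot's components are meant to be reused in a larger trial and possibly in routine programs, so an unresolved criterion would carry forward.

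**Working it through.** No arithmetic applies. The plan attaches no figure to this criterion, so there is nothing to reproduce, and the check is a comparison of the two statements.

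**Step 1: the qualifiers.** The exclusion list limits the rule in three ways: the disease must be *significant*, *severe* and *epicardial*. The risk section has none of these limits. Neither section defines *significant* or *severe*, by degree of stenosis, by vessel or otherwise.

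**Step 2: each type of patient under each statement.**

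| Coronary status | Exclusion list | Risk section |
|---|---|---|
| (a) No coronary disease, or fully revascularized | Not excluded | Not excluded |
| (b) Un-revascularized, significant, severe and epicardial | Excluded | Excluded |
| (c) Un-revascularized, but outside at least one qualifier | Not excluded | Excluded |

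The statements agree on (a) and (b) and conflict on (c). They are nested: everyone the list excludes is also excluded by the risk section.

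**Step 3: which statement is applied.** Both descriptions of screening point to the inclusion and exclusion criteria. Neither sends the coordinator to the risk section. Followed as written, the chart review lets a group (c) patient through. No sentence ranks the two statements, tells staff to combine them, or calls one a summary of the other.

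**Step 4: whether another safeguard closes the gap.** The cardiologist's exclusion is a general judgement of high risk and names no coronary criterion. A group (c) patient who is not judged high risk stays in. The catheterization could supply the relevant findings, but with no threshold stated it cannot decide between the two rules. The document also does not say whether it must be complete before randomization.

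**Step 5: whether the enrolled population could be described afterwards.** The visit chart collects diagnosis codes and pre-existing conditions at intake. It has no entry for catheterization findings or grade of coronary disease, so the data as planned may not separate (a) from (c).

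**Step 6: size.** On sample size, the plan says "Thirty five subjects will be randomized to each group", which is 2 × 35 = 70 subjects. It gives no proportion of candidates in group (c), so the number affected cannot be derived.

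**The case against.** The strongest reply is that this is a matter of wording with little consequence. Because the two rules are nested, both can be obeyed at once. The risk-section sentence may be shorthand for the listed criterion. The examining cardiologist can exclude high-risk patients. The exclusion list separately removes anyone with other conditions that the principal investigator and therapy staff consider unsafe for the walk test or conditioning. Sessions are supervised, and angina is listed as a reason to stop and assess.

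Part of this stands. The further safeguards are real and narrow the safety consequence. They do not reconcile the two statements. Obeying both would resolve group (c), but no text tells staff to do so. If the sentence is shorthand, the document does not say so, and the risk section then overstates the protection and still needs correction.

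The reply also rightly blocks several stronger readings that a reader might infer:

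- *That the plan does not define who is enrolled.* Only group (c) is in dispute. The other eligibility criteria are untouched.
- *That two screeners would routinely decide the same patient differently.* Both screening passages point to the list, which makes it the likely working rule. The better-supported worry is that the broader sentence is not applied at all.
- *That a sizeable share of the 70 subjects is affected.* The document offers no basis for any percentage.
- *That the treatment comparison is biased.* Subjects are randomized at the end of the Intake Assessment, after eligibility is settled, so either rule acts on both arms alike.

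**Conclusion.** The point holds in a limited form. The exclusion list and the risk section give different coronary exclusions, and they disagree for patients with un-revascularized disease outside the list's qualifiers. Those patients pass the check that the plan prescribes and are barred by the safeguard that it describes. What is at stake is whether the stated risk mitigation matches the patients who are exercised, and which population the conclusion on Hypothesis 1 describes.

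The size of the subgroup is unknown and cannot be bounded usefully from the document. No alpha, power or sample-size figure changes.

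The conclusion assumes that staff screen as the two screening passages direct, and that no precedence rule exists outside this document. If local practice already applies the broader sentence, the effect on enrolment disappears, but the text remains inconsistent. The matter should be corrected because it concerns a stated protection for participants and the correction is cheap.

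**What to change.** 1. The clinical team should reconcile the two statements and put one identical wording in the exclusion list and the risk section. This review takes no position on which rule is right.
2. Define the chosen terms operationally, so that a screener can apply them to a catheterization report. Identical wording alone would not suffice if *significant* and *severe* stay undefined.
3. Screen on that wording, and state that the findings needed to apply it must be available before randomization.
4. Record coronary status at screening, taken from the catheterization already in the work-up, and tabulate it by arm with the baseline data. If subjects have already been enrolled, abstract it from their records, so that the report can say how many had un-revascularized disease and of what grade.
5. Check the consent form against the reconciled wording and change it if needed.

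The cost is a protocol correction of a sentence or two, possibly a consent revision, and one added item on the case report form. No new test and no change to the analysis is required.
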